- The participant's personal data will be collected. The data include the participant's name, age, address, weight, height, and phone number.
- All subjects of both groups will be tested for the isokinetic parameters twice (on dominant and non-dominant sides).
- The participant will be allowed to sit on the adjustable seat of the isokinetic dynamometer system.
- The tested arm will be placed on the limb support pad and secured with strap. Then the tested hand will be securely fastened with wrist attachments.
- The dominant hand is the one preferred by the participant to write or manipulates objects.
- Shoulder and waist straps will be placed around the chest to secure and stabilize the patient. In addition, the untested limb will be placed in a rest position and secured by strap,

Measurement of muscle performance of wrist by isokinetic dynamometer

This involves:

- 1) Measuring peak torque of wrist extensor and flexor muscles /body weight among Egyptian physical therapy students.

- 2) Measuring extensor / flexor wrist muscles ratio among Egyptian physical therapy students.
- 3) Measuring wrist extensor and flexor muscles endurance among Egyptian physical therapy students.

1- pre-experimental testing instructions:

- Before the actual isokinetic testing procedures, each participant will perform one practice series of three sub-maximal wrist extension and flexion repetitions to get accommodated with the specificity of the isokinetic speed of movement and wrist ROM. That will be done to minimize any practice effect during the actual testing procedure.

2- The isokinetic system preparation:

- The isokinetic system was powered, initialized, and calibrated.
- The dynamometer was rotated to 0° and was tilted to 0°.
- Wrist Attachment of dynamometer will be attached by placing input tube on dynamometer then it will be rotated horizontally to the floor to be aligned with the dynamometer shaft red dot.
- The testing chair was rotated to 0° degrees and seat back tilt was set to 85 degrees.
- The participant sat on the chair and the wrist axis of rotation will be aligned with dynamometer lever arm as discussed later in participant preparation.
- Axis of rotation for this pattern lies between the proximal row of the carpal, at the capitate bone, and the radius at the radiocarpal joint.
- The isokinetic parameters will be tested at angular velocity of 60°/sec. The testing velocity was selected from the control panel. The rationale for choosing this speed was based on previous studies. The literature suggested that wrist measurements will be taken from each participant at

the points where the dynamometer equipment was adjusted at 60°/sec for measuring muscle strength and 180°/sec for measuring muscle endurance angular velocities (**Janicijevic et al., 2020**). Fast speed is for power, whereas slow speed is for strength. Reports by researchers have been employing both 60° and 120°/sec in isokinetic assessment for strength and power.

- Before being raised to this position, the dynamometer's range of motion will be adjusted to a total of 80 degrees, comprising 40 degrees of wrist flexion and 40 degrees of wrist extension (**Seven et al., 2019**).
- The concentric/concentric mode was used to measure the wrist muscles peak torques, power and endurance.

B. Experimental phase

This phase involved experimental testing procedures for measuring peak torque of wrist extensor and flexor muscles /body weight, extensor / flexor wrist ratio and wrist extensor and flexor muscles endurance among Egyptian physical therapy students.

The experimental testing procedures will be conducted for all the participants of both groups.

- Following warm up, each participant will be positioned according to the instruction described before.
- The personal data of each participant will be introduced into computer, which includes participant name, age, sex, identification number and weight.
- The test protocol that will include the wrist ROM, the testing velocities, the mode of contraction and the test repetitions will be selected from the control panel.
- Each participant will be instructed to perform five sets of wrist extension and flexion at the selected wrist ROM (60°).

- Verbal encouragement will be given during the testing procedure to maximize the participant's voluntary effort.
- Wrist extensors and flexors will be tested at the concentric mode of muscle contraction using 60°/sec angular velocity.
- A 1- min rest will be given between warm up and actual test sequence.
- Testing procedures will be performed twice, on the dominant and non-dominant sides for both the study and control groups.

C. Analysis of the captured data

After performing isokinetic testing, the final output data were displayed after being processed by the relevant isokinetic software in the form of tables and graphs. The peak torque normalized for Bodyweight (Nm/Kg) for the wrist extensors and flexors/body weight were used to calculate the wrist flexor/extensor muscles strength ratio

$$\text{Wrist strength ratio} = \frac{\text{Peak torque of wrist flexors}}{\text{Peak torque of wrist extensors}}$$

Data Analysis:

The statistical measure will be performed through the statistical package for social sciences (SPSS) version 25 for windows. It will be intended to compare between the experimental and control groups for the wrist flexors/extensors strength ratio for both dominant and non-dominant sides.

Statistical Analysis:

- The statistical measure will be performed through the statistical package for social sciences (SPSS) version 25 for windows.
- Descriptive statistics in the form of mean and standard deviation will be used.

- Unpaired T-test will be used to investigate the comparison between two groups for numerical data.
- Chi-Square will be used to investigate the comparison between two groups for categorical data.
- One way between subjects' multivariate analysis of variance (One-way MANOVA) is useful in experimental situations where at least some of the independent variables are manipulated.
- The alpha point of 0.05 will be used as a level of statistical significance

References

Abichandani, D., & Parkar, B. (2017). Comparison of upper limb proprioception in chronic mechanical neck pain patients with age-sex matched healthy normal. *International Journal of Physiotherapy and Research*, 5(6), 2466-2473. <https://doi.org/10.16965/ijpr.2017.191>

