Isokinetic Assessment of Wrist Muscles Performance among Egyptian Physical Therapy Students with Chronic Non-Specific Neck Pain

Thesis

Submitted to the Department of Biomechanics in Partial Fulfillment of the
Requirements for the Master Degree in Physical Therapy

By

[name]

Teaching Assistant, Department of Biomechanics,
Faculty of Physical Therapy, Kafr El Sheikh University
B.Sc., Physical Therapy, Cairo University, 2018

Supervisors

[name] [name]

Professor and Head of Physical Therapy Department
of Musculoskeletal Disorders and Its Surgery
Physical Therapy Department of Musculoskeletal
Disorders and Its Surgery
Faculty of Physical Therapy
Cairo University

[name] [name]

Professor and Head of Biomechanics
Department
Biomechanics Department
Faculty of Physical Therapy
Kafr El Sheikh University

[name] [name]
Lecturer of Biomechanics
Department of Biomechanics
Faculty of Physical Therapy
Cairo University

**Faculty of Physical Therapy
Cairo University
2024**

Data analysis and statistical design

Data were expressed as mean \pm SD. Unpaired t-test was used to compare between subjects characteristics of the two groups. One way MANOVA was used to compare measured variables between the two groups. Statistical package for the social sciences computer program (version 20 for Windows; SPSS Inc., Chicago, Illinois, USA) was used for data analysis. *P* less than or equal to 0.05 was considered significant.

CHAPTER IV

RESULTS

The main aim of this study was to assess the effect of chronic non-specific neck pain on peak torque of wrist extensor and flexor muscles /body weight, extensor / flexor wrist ratio and on wrist extensor and flexor muscles endurance among Egyptian physical therapy students.

Demographic data of subjects:

A total of 44 students participated in this study; they were assigned into 2 equal groups, Group A, study group, was include twenty two students with chronic non-specific neck pain (CNSNP) and Group B, control group, was include students without CNSNP.

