Using G-power software (version 3.1.9.7; Franz Faul, Universitat Kiel, Germany) for windows and regarding MANOVA study, alpha level of 0.05, confidence level 0.80, and effect size 0.56, calculated from the previous study of (**Agirman et al., 2017**) that used the isokinetic dynamometer for measuring the peak torque of wrist with a sample of 35, and a two-sided alternative hypothesis, the sample size is 39 patients to be able to reject the null hypothesis. If 15% dropout rate is anticipated, approximately 44 patients (twenty-two in each group) will be recruited.

1. Students' selection:

The current study will be conducted on twenty-two non-specific neck pain Egyptian physical therapy students a with referral from orthopedic surgeons by diagnosis with non-specific neck pain other twenty-two without neck pain subjects from outpatient clinic of Faculty of Physical Therapy, EL DELTA University. Students' age ranges from 18 to 23 years. Students will be selected from faculties of physical therapy. Students will be assigned into two equal groups, the study group (GA) (chronic non-specific neck pain students) and the control group (GB) (normal students). They will be instructed not to participate in any training program until the posttest.

Inclusion criteria:

- 1- Students from both genders (**Fayez, 2014**).
- 2- Duration of the non-specific neck pain is more than 3 months (for symptomatic group with no neurological manifestations and with referral from orthopedic surgeons by diagnosis with non-specific neck pain) and for matched students, they do not have any history of neck pain (**Chung & Jeong, 2018**)
- 3- Student' age ranges from 18 to 23 years.
- 4- Neck pain intensity on the numerical Pain Rating Scale will be between 3 to 8.
- 5- Neck pain-related disability on the Neck Disability Index will be between 5-14points (10 – 28%) mild disability and 15-24points (30-48%) moderate disability.
- 6- Body mass index for students will not be less than 18.5 and not more than 29.5 (**Alasadi, 2018**).

Exclusion Criteria:

Any participant suffered from one of these symptoms will be excluded:

- 1- Indications of neurological conditions (i.e., Parkinson's disease, multiple sclerosis, head injury, peripheral neuropathy, stroke, or nerve root entrapment) (**Mahmoud et al., 2020**).
- 2- Headache caused by a certain diagnosis of headache.
- 3- History of cancer, infection, or any other illness symptoms.

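### Recruiting 44 covers about 11% dropout from the required 39, not the stated 15%, and the 0.80 labelled a confidence level must be power (minor)

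*Combined protocol and SAP*

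**What the plan says.** The Sample size calculation (combined protocol and SAP, Chapter III) describes a G-power calculation for a MANOVA with "alpha level of 0.05, confidence level 0.80, and effect size 0.56". The effect size is taken from an earlier isokinetic study of the wrist. The paragraph concludes that "the sample size is 39 patients to be able to reject the null hypothesis", and then adds the loss allowance: "If 15% dropout rate is anticipated, approximately 44 patients (twenty-two in each group) will be recruited". It does not use the word power.

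Two other places bear on the point. The Statistical Analysis section of the same document repeats the significance level: "The alpha point of 0.05 will be used as a level of statistical significance". The SAP, under the demographic data of subjects, reports the number achieved: "A total of 44 students participated in this study", in two equal groups.

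**The concern.** A dropout allowance is meant to ensure that, if the anticipated loss occurs, the required number is still available for analysis. Here the required number is 39 and the anticipated loss is 15%, so 85% of those recruited should come to at least 39. With 44 recruited they do not. The paragraph therefore claims a protection that the sample does not have.

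The second slip is in the label. A prospective sample size calculation needs a power, and none is named. The only figure that could be the power is printed as "confidence level 0.80". Taken literally, a confidence level of 0.80 contradicts the alpha in the same sentence. What is at stake is whether the paragraph is accurate and can be read correctly, not the choice of analysis.

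**Working it through.** **Inputs.** From the Sample size calculation: required total 39, anticipated dropout 15%, recruited total 44 (22 + 22), alpha 0.05, a figure of 0.80, effect size 0.56, MANOVA. From the Statistical Analysis section: alpha 0.05. From the SAP: 44 participated.

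**Step 1. Where 44 probably comes from.** Adding 15% to the required number gives 39 × 1.15 = 44.85. Taken down to an even total, so that the groups are equal, this is 44. The document does not show this step; it is an inference. Multiplying by 1.15 is not the right inflation, because the 15% is lost from those recruited and not from the 39.

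**Step 2. What 15% loss leaves.** 44 × 0.85 = 37.4, so about 37 and two short of 39. In whole people, 15% of 44 is 6.6. Seven losses leave 37, and even six leave 38.

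**Step 3. What 15% would need.** Recruited N = required n / (1 − dropout) = 39 / 0.85 = 45.88, rounded up to 46, or 23 per group.

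| Recruited | Left after 15% loss | Largest loss that keeps 39 |
|---|---|---|
| 44 | 37.4 | 5/44 = 11.4% |
| 45 | 38.25 | 6/45 = 13.3% |
| 46 | 39.1 | 7/46 = 15.2% |

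**Step 4. What 44 covers.** (44 − 39) / 44 = 11.4%. Expressed on the 39 instead, 5/39 = 12.8%. Neither is 15%.

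**Step 5. The label.** Confidence is 1 − alpha = 1 − 0.05 = 0.95. A confidence level of 0.80 would imply alpha = 0.20, against the 0.05 given in both sections. With alpha already fixed, 0.80 can only be the power.

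**Step 6. Is 39 compatible with power 0.80?** The paragraph does not say whether 0.56 is f or f², or how many response variables (p) were entered, so both are assumptions here. For a two-group MANOVA, power comes from the noncentral F with p and N − p − 1 degrees of freedom and noncentrality N × f².

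- 0.56 read as f (f² = 0.3136), p = 3: the smallest N with power 0.80 is 39 (power 0.801), an exact match. At N = 37 power is 0.775; at N = 44 it is 0.856.
- 0.56 read as f²: p = 9 gives N = 38, and p = 10 gives N = 40 (power 0.798 at 39).

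So 39 is attainable at power 0.80, which also supports reading the 0.80 as power.

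**The case against.** The case for leaving the paragraph alone has four parts.

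- The text says approximately 44, and 44 is within two of the correct 46.
- The design is cross-sectional, so there is no follow-up period in which participants drop out; losses would be incomplete or unusable tests.
- The SAP reports 44 participants, above the 39, so no shortfall is visible.
- Had only 37 remained, power would have gone from 0.801 to 0.775 under the reading that reproduces 39.

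All of this stands, and it is why the point is minor. It does not make the sentence correct. The total is pinned down as 22 per group, the rounding goes down when a required minimum should be protected by rounding up, and 15% is not reached on any of the calculations above.

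A reader might go further and infer that the study was underpowered, or that 39 is itself wrong. The documents do not support either inference. The missing effect-size metric and variable count mean that 39 cannot be confirmed uniquely, but at least one plain reading returns it exactly. A reader might also take 0.56 as a standardised mean difference, for which a single outcome at N = 39 has power of only about 0.40. The paragraph does not say that; it sizes the study for a MANOVA, and that reading would call for about 102 participants, not 39. Nor does the wording show that a test at 80% confidence was intended, since 0.05 is stated in both sections.

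**Conclusion.** The paragraph is wrong as written on two small points. Recruiting 44 protects the required 39 against five losses (11.4%), not against 15%. A 15% loss would leave about 37, two short, and covering it would have taken 46. The figure of 0.80 is the power, misnamed.

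The dropout conclusion rests only on the document's own 39, 15% and 44, read as a loss from those recruited. The label conclusion rests on the stated alpha. Neither depends on how the effect size of 0.56 is interpreted. Severity is minor: 44 students are reported as taking part, and nothing here shows the target of 39 to be wrong or the study to lack power.

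**What to change.** In the Sample size calculation, keep the 39, the 44 and the source of the effect size, and make two edits.

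1. Replace "confidence level 0.80" with: *power 0.80*.
2. Replace the dropout sentence with: *Recruiting 44 (22 per group) allows 5 participants (about 11%) to be non-evaluable while keeping the required 39; a 15% loss would leave about 37 and would have needed 46.*

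Optionally, and as documentation only, state from the G-power output whether 0.56 is f or f² and how many response variables were entered. If the output was not kept, say so; the two edits above do not depend on it.

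The cost is the rewording of one paragraph. The stated allowance falls from 15% to about 11%. No participants are added and the analysis does not change.

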As shown in table (1) and figures (1-4); the mean values of age of groups A and B were (20.6 ± 1.8) and (20.5 ± 1.7) years respectively, and of weight were (68.6 ± 10.7) and (72.1 ± 12.5) kg respectively, the mean values of height of groups A and B were (170.5 ± 7.8) and (171.2 ± 10.3) cm respectively, and of BMI were (23.4 ± 2.4) and (24.7 ± 3.1) kg/m^2 respectively. There were no significant differences between both groups of mean age, weight, height and BMI ($p > 0.05$).

Table (1): Subjects characteristics of both groups

Measurd variable	Group A Mean \pm SD	Group B Mean \pm SD	t-value	p-value
Age (years)	20.6 ± 1.8	20.5 ± 1.7	0.085	0.933
Weight (kg)	68.6 ± 10.7	72.1 ± 12.5	-1	0.314
Height (cm)	170.5 ± 7.8	171.2 ± 10.3	-0.247	0.806
BMI (kg/m^2)	23.4 ± 2.4	24.7 ± 3.1	-1.47	0.149

[figure not shown]

Fig 1: mean values of subjects age of both groups

[figure not shown]

Fig 2: mean values of subjects weight of both groups

[figure not shown]

Fig 3: mean values of subjects height of both groups

[figure not shown]

Fig 4: mean values of subjects BMI of both groups

Normality test:

Data were screened for normality assumption, homogeneity of variance, and presence of extreme scores. Shapiro-Wilk test for normality showed that all measured variables are normally distributed, so one way

MANOVA for between groups' comparison and Pearson coefficient correlation for finding the relation between variables were used.

Table (2): Comparison of mean values of measured variables between groups.

Work fatigue (%)				
Flexion 60°/sec	15.96 ± 16	13.8 ± 15.7	2.16	0.658
Flexion 180°/sec	14.5 ± 33	4.14 ± 26	10.36	0.260
Extension 60°/sec	8.4 ± 16	0.25 ± 15	8.15	0.095
Extension 180°/sec	4.95 ± 25	1.6 ± 36	3.35	0.725

II- Effect of CNSNP on work fatigue:

As shown in table (2) and demonstrated in figures (7 and 8), the mean values \pm SD of work fatigue of wrist flexion at (60 and 180°/sec) for subjects in groups A and B were (15.96 \pm 16 and 14.5 \pm 33) and (13.8 \pm 15.7 and 4.14 \pm 26) % respectively. The mean values \pm SD of work fatigue of wrist extension at (60 and 180°/sec) for subjects in groups A and B were (8.4 \pm 16 and 4.95 \pm 25) and (0.25 \pm 15 and 1.6 \pm 36) % respectively. There was statistical non-significant difference in the mean values of work fatigue of wrist flexion and extension at 60 and 180°/sec between both groups ($P>0.05$).

[figure not shown]

Fig 7: mean values of wrist flexors work fatigue of the two groups

[figure not shown]

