Wrist isokinetic dynamometry has been widely used to evaluate muscle function and identify the presence of muscular imbalances in the wrist joint, particularly in individuals with upper limb disorders and injuries (**Seven et al., 2019**). The assessment of wrist isokinetic strength has been shown to be a reliable and valid tool for evaluating the strength and endurance of wrist flexors and extensors in both clinical and research settings (**Ağırman et al., 2017**).

Although it is widely acknowledged that chronic non-specific neck pain is linked to hand disability, the assessment of flexor/extensor wrist strength ratio in this group has only recently gained attention. Furthermore, there is limited research investigating the strength control ratio that incorporates both concentric and eccentric muscle actions, and additional scientific evidence is needed to establish the relationship between chronic non-specific neck pain and upper limb disability, therefore in our study, we will be conducted to examine wrist muscle performance through peak torque of wrist extensor and flexor muscles to body weight, extensor / flexor wrist strength ratio and wrist extensor and flexor muscles endurance in chronic non-specific neck pain among Egyptian college students to evaluate functional ability of wrist in the upper limb in non-specific neck pain students to set new assessment and rehabilitation goals. This will subsequently be translated into home therapy program, contributing to decrease the burden of neck pain economically and on health care management.

Chapter III

[figure not shown]
Subjects and methods

Our study aims to evaluate peak torque of wrist extensor and flexor muscle / body weight and extensor / flexor wrist ratio and wrist extensor and flexor muscle endurance among Egyptian physical therapy students with chronic non-specific neck pain. The practical part of the study is expected to be from May/2023 to December/2023 and will be conducted in the isokinetic lab in EL DELTA University.

Design: cross-section study

Sample size calculation:

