- All the subjects will be included according to inclusion and exclusion criteria and they will be selected from outpatients clinics of EL DELTA University. Then, after taking their individual demographic data, they will be assigned into two groups, the study group (GA) (chronic non-specific neck pain subjects without neurological manifestations) and the control group (GB) (normal subjects). After that, they will sign an informed consent form after receiving a brief orientation session about the nature of the study, the study purpose, procedure, possible benefits, and risks with preserving each subject privacy.

Measurement of craniocervical angle to exclude subjects with abnormal forward head posture

Non-specific neck pain students will be evaluated to assess forward head posture by photographic posture analysis method by placing two markers on the ground separated by 1.5 m, where the smartphone and the subject will be located. Reference markers will be placed on the spinous process of C7 and in the swallow of the subjects' ears, which will be identified through palpitation. The subject will be placed on the floor mark, barefoot and standing, lateral to the evaluator. At this point. The evaluators will be experienced and trained physiotherapists (**Gallego-Izquierdo et al., 2020**). The ones calculated with the FHP app will be classified attending to the presence or not of FHP. The presence of FHP (FHP group) will be determined by an angle value lower than 50, and the absence of FHP (no-FHP group) if the angle value will be greater than or equal to 50 (**Lee et al., 2015**).

Assessment of pain intensity by Numerical Pain Rating Scale

Also they will be evaluated to assess pain intensity by Numerical Pain Rating Scale (**Appendix II**) as The Numeric Pain Rating Scale (NPRS) is a unidimensional measure of pain intensity in adults, including those with chronic pain due to rheumatic diseases. (man in pain, R) The NPRS is a segmented numeric version of the visual analog scale (VAS) in which a respondent selects a whole number (0–10 integers) that best reflects the intensity of his/her pain. The 11-point numeric scale ranges from '0' representing one pain extreme (e.g., "no pain") to '10' representing the other pain extreme (e.g., "pain as bad as you can imagine" or "worst pain imaginable"). As inclusion criteria, Neck pain intensity on the numerical Pain Rating Scale will be between 3 to 8.

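### Controls are labelled matched, but the plan describes no matching and compares the groups unpaired and unadjusted, so comparability rests on non-significant t-tests

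*Combined protocol and SAP*

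**What the plan says.** The design is given in Chapter III of the combined protocol and SAP as "Design: cross-section study". Inclusion item 2 sets the pain-duration rule for the symptomatic group and then adds, for the other group, "for matched students, they do not have any history of neck pain". That is the only place where this study's controls are called matched.

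Participant preparation says of the recruits that "after taking their individual demographic data, they will be assigned into two groups", the two groups being students with and without chronic neck pain. Age and BMI appear as eligibility limits, for example "Student' age ranges from 18 to 23 years", and BMI 18.5 to 29.5. Both sexes may enter.

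For analysis, the Statistical Analysis section states "Unpaired T-test will be used to investigate the comparison between two groups for numerical data", plus chi-square for categorical data and a one-way between-subjects MANOVA. The SAP (Data analysis and statistical design) reports "One way MANOVA was used to compare measured variables between the two groups", and unpaired t-tests for subject characteristics. Neither document names a pair term, stratum or covariate. Under Demographic data of subjects, the SAP concludes: "There were no significant differences between both groups of mean age, weight, height and BMI".

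**The concern.** This is an observational comparison of two groups defined by pain status. Calling the controls matched tells a reader that some confounding was removed by design, and that claim needs a named factor, a procedure and an analysis that respects it. None is described, so the reader cannot tell what, if anything, was balanced.

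Without matching or adjustment, the case for comparability comes down to P > 0.05 in Table 1. Failure to reject with 22 per group is weak evidence of balance. Sex is missing from the table altogether, although both sexes are eligible and the protocol's own background text reports that neck discomfort and wrist symptoms are more common in women. What is at stake is how far a group difference, or its absence, can be attributed to neck pain.

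**Working it through.** **Matching in the text.** The places where matching would have to appear compare as follows.

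- Inclusion item 2: the word is used, with no factor.
- Delimitations, Students' selection and Participant preparation: groups follow pain status; no pairing step.
- Inclusion items on age and BMI: common limits for all students, which is restriction.
- Sample size calculation: a MANOVA calculation with no mention of pairs.
- Statistical Analysis, and the SAP's analysis section: unpaired tests, group only.
- The reference list contains a cited study with age-sex matched controls. That is the cited study's title and does not describe this one.

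**Table 1, BMI, reproduced first.** Inputs from the SAP: 23.4 ± 2.4 (group A), 24.7 ± 3.1 (group B), 22 per group, printed t = -1.47, P = 0.149.

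- Pooled SD = sqrt((2.4² + 3.1²)/2) = 2.772.
- SE = 2.772 × sqrt(2/22) = 0.836.
- t = -1.3/0.836 = -1.56 on 42 df, P = 0.127. Rounding of the printed means and SDs allows |t| from 1.41 to 1.71, which contains 1.47. A t of -1.47 on 42 df gives P = 0.149, so the printed row is consistent.

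**Size of the BMI difference.**

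- From the printed means and SDs: 1.3/2.772 = 0.47 (0.43 to 0.51 allowing for rounding).
- From the printed t: 1.47 × sqrt(2/22) = 0.44.
- 95% CI: -1.3 ± 2.018 × 0.836 = -2.99 to 0.39 kg/m².

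**Other rows of Table 1** (absolute standardised differences from printed means and SDs): weight 0.30, height 0.08, age 0.06. Sex has no row. The narrative and Figures 1 to 4 cover the same four variables.

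**What P > 0.05 can show here.** The t-test is significant only if the observed standardised difference exceeds 2.018 × sqrt(2/22) = 0.61. Any observed imbalance up to that size would be reported as no significant difference.

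**Possible effect on an outcome.** If an outcome has within-group correlation ρ with BMI, the imbalance alone shifts the group difference by about ρ × 0.44 to ρ × 0.47 SD. The documents give no ρ. Over an assumed range of 0 to 0.5, the shift runs from 0 to 0.5 × 0.47 = 0.23 SD, with its direction set by the sign of ρ. This is an illustration, not an estimate.

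**The case against.** The strongest reply is that the word is loose usage for a comparable group. Both groups are physical therapy students within the same narrow age and BMI limits and under the same exclusions, and the sample size and tests are between-subjects. This is the most natural reading of the text, and it stands. It supports deleting the word, because common limits do not balance a factor within them.

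A second reply is that size is already handled. Peak torque is divided by body weight, the strength outcome is a ratio, and the background text defines work fatigue as a within-person percentage change. This stands against one tempting inference, that work fatigue is confounded because it is not scaled to body weight. Residual dependence on BMI or sex remains possible, but the documents do not quantify it.

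Two stronger readings also fail:

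- *The BMI gap shows that matching failed.* BMI is never named as a matching factor, and P = 0.149 is compatible with chance.
- *Pairs were ignored, so a reported null is an artefact.* If pairs existed with positive within-pair correlation r, the unpaired test would be conservative. For extension fatigue at 60°/sec (8.4 ± 16 v 0.25 ± 15, printed P = 0.095), assuming r = 0.3, the paired SE is sqrt(16² + 15² - 2 × 0.3 × 16 × 15)/sqrt(22) = 3.91. That gives t = 2.08 on 21 df and P = 0.0497; at r = 0.2, P = 0.065. But nothing indicates that pairs were formed, r is not given, and rounding alone moves the unpaired P from 0.095 to 0.089. Nor can the reported summaries be called wrong: they are means and SDs, which pairing does not change, and no standard errors or intervals are printed.

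Finally, choosing BMI as a covariate after seeing Table 1 is data-driven. That is fair, and is why the adjusted analysis must be labelled and shown beside the unadjusted one.

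**Conclusion.** The point holds as a mismatch between label and design, joined to an unadjusted comparison. The controls are called matched once, the described design shows restriction only, and comparability is inferred from non-significance at 22 per group. BMI differs by 0.44 to 0.47 SD, with an interval reaching about -3.0 kg/m², and balance on sex cannot be judged.

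The documents do not show that matching was attempted and failed, or that any outcome is biased; a bias would depend on correlations they do not report. The absence of a matching step is judged on the available text, as a part near the start of the combined document was not in the copy reviewed. The standardised differences rest on rounded means and SDs. The defect does not invalidate the study, but it should be corrected, because adjustment for variables already recorded is better in a non-randomised comparison than a group-only model.

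**What to change.** 1. In inclusion item 2, delete the matching word and describe the controls as unmatched students with no history of neck pain who meet the same age and BMI limits. Only if pairs were in fact formed, name the factors and the procedure, keep the pair identifier and analyse within pairs.
2. Add sex, age and BMI beside group in the MANOVA and its univariate rows. Age and sex are entered at testing, and BMI is already in Table 1. Report the adjusted result next to the unadjusted one, and label it post hoc where results are already known. Say why BMI is included for torque already divided by body weight.
3. In Table 1, add a row for sex and a column of standardised differences, and remove the inference of comparability from P > 0.05.

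Cost: a wording change, a re-run and a revised table, with no new data. The univariate error degrees of freedom fall from 44 - 2 = 42 to 44 - 5 = 39. The remaining drawback is that the covariates are chosen after the data were seen, which the labelling discloses but does not remove.
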